45. **PK Sampling - Week 8, Week 12, and Follow-up Visit:** A single 2 mL blood sample for PK analysis of trametinib, dabrafenib and its metabolites (hydroxy-dabrafenib and desmethyl-dabrafenib) will be collected at Week 8 (pre-dose), Week 12 (pre-dose), and at the Follow-up Visit. Subjects with morning clinic visits are to be instructed to withhold their morning doses of study treatment and PK samples will be collected prior to dabrafenib administration. Subjects with afternoon clinic visits are to be instructed to take their morning doses as usual and PK samples will be collected 4 to 8 hrs following dabrafenib administration. **Samples at the Follow-up Visit are no longer requested for collection as of Protocol Amendment 11.**

[REDACTED]

- 
54. **STUDY TREATMENT:** Subjects must receive their supply of study treatments within 3 days of enrollment.
55. **FOLLOW-UP VISIT:** The Follow-up Visit should take place within 28 days (+7 days) of the last dose of study treatments. If the subject is unable to return to clinic, site staff is encouraged to call subject for assessment of AEs.
56. **FOLLOW-UP VISIT:** All safety and laboratory assessments should be performed unless the assessments were performed within 4 weeks prior to the Follow-up Visit.
57. **FOLLOW-UP VISIT:** If the last cardiac assessment was >12 weeks prior to the Follow-up Visit, an ECHO should be performed.
58. **EXTENDED FOLLOW-UP:** The following evaluations will be performed for all patients in all cohorts.
- a) Dermatologic exam. Exams will be performed every 4 weeks (+/-7 days) for the first 6 months. The skin will be carefully examined and pictures and biopsy will be taken of any new or changed skin lesions.
 - b) If study treatments are permanently discontinued prior to the subject having confirmed disease progression, the subject will continue to have disease assessments every 12 weeks (+/-14 days) until disease progression or initiation of new anti-cancer treatment, or death, whichever comes first.
 - c) Subjects will be followed every 12 weeks (+/-14 days) for survival until the subject dies or withdraws consent or is lost to follow up, or up to a time period as defined in Section 16.3. Survival follow up may be performed via clinic visit, a telephone contact, an email or by mail. The initiation of any new anti-cancer treatment(s) and date of last contact should also be documented.
 - d) Subjects will have a head and neck exam performed every 12 weeks for the first 6 months to monitor for secondary or recurrent malignancy.
 - e) Subjects may have CT and/or MRI scans of the chest and abdomen for up to 6 months to monitor for secondary or recurrent malignancy.

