6.3.1.1 Administration and Storage of Dabrafenib Capsules

Administration: Dabrafenib capsules must be dispensed only to subjects enrolled in the study and in accordance with the protocol. Dabrafenib should be administered under fasted conditions, either 1 hr before or 2 hrs after a meal with approximately 200 mL of water. Subjects should be encouraged to take their doses at 12 hr intervals and at similar times every day.

Missed Dose: If a subject misses a dose of dabrafenib, the subject may take the dose immediately if the next dose is scheduled for at least 6 hrs later. If the next scheduled dose is due in less than 6 hrs, the subject should skip the dose and resume dosing at the next scheduled dose.

Storage: Dabrafenib must be stored in a secure area under the appropriate physical conditions for the product. Access to and administration of the dabrafenib will be limited to the investigator and authorized site staff.

Dabrafenib is to be stored and dispensed in an opaque bottle. The recommended storage conditions for dabrafenib are stated on the product label. Maintenance of a temperature log (manual or automated) at the site is required.

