6.3.2.1 Administration and Storage of Trametinib Tablets

Administration: Trametinib must be dispensed only to subjects enrolled in the study and in accordance with the protocol. Trametinib should be administered under fasted conditions, either 1 hr before or 2 hrs after a meal with approximately 200 mL of water. Subjects should be instructed to take their dose of trametinib concurrently with the morning dose of dabrafenib.

Vomiting: If a subject vomits after taking study treatment, the subject should be instructed not to retake the dose but should be instructed to take the next scheduled dose.

Missed Dose: If a subject misses a dose of trametinib, the subject may take the dose immediately if the next dose is scheduled for at least 12 hrs later. If the next scheduled dose is due in less than 12 hrs, the subject should skip the dose and resume dosing at the next scheduled dose.

Storage: Trametinib must be stored in a secure area under the appropriate physical conditions for the product. Trametinib is to be stored at the temperature specified on the label. Maintenance of a temperature log (manual or automated) is required. Access to and administration of trametinib will be limited to the investigator and authorized site staff. Refer to the SPM for further detailed instructions on IP storage.

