38. **MM ONLY:** BM aspirate and BM biopsy samples will be assessed by IHC, flow cytometry, FISH and cytogenetics **within 90 days prior enrollment**.

39. **MM ONLY:** Flow cytometry for plasma cell enumeration and phenotyping will be performed on BM aspirate and BM biopsy samples at Week 8 and then at the time of achieving a CR or best response. **NOTE:** Density gradient is not recommended.
40. **MM ONLY:** SPEP should be performed **within 28 days prior to enrollment**, every 4 weeks for the first 48 weeks of study treatment, then every 12 weeks thereafter, and at the Follow-up Visit.
41. **MM ONLY:** UPEP must be performed using a 24-hr urine sample.
42. **MM ONLY:** If UPEP is positive at Screening (**or within 28 days prior to enrollment**), then a UPEP should be performed every 4 weeks for first 48 weeks of study treatment, then every 12 weeks thereafter, and at the Follow-up Visit.
43. **MM ONLY:** CRP, β 2 microglobulin; immunoglobulins (IgG, IgA and IgM) and serum FLC assay should be performed **within 28 days prior to enrollment**, every 4 weeks for the first 48 weeks of study treatment, then every 12 weeks thereafter, and at the Follow-up Visit.
44. **PK Sampling - Week 4:** Two 2-mL blood samples for PK analysis of trametinib, dabrafenib and its metabolites (hydroxy-dabrafenib and desmethyl-dabrafenib) will be collected at Week 4. **For subjects with a morning clinic visit:** Subjects will be instructed to withhold their morning doses of study treatment prior to the study visit. The first PK blood sample (pre-dose) will be obtained prior to dabrafenib administration (between 8 to 14 hrs after the evening dose of dabrafenib on the previous day). The second PK blood sample (post-dose) will be obtained 1 to 3 hrs following administration of dabrafenib. **For subjects with an afternoon clinic visit:** Subjects will be instructed to take their morning doses of study treatments as usual. The first PK blood sample (pre-dose) will be obtained 4 to 8 hrs following dabrafenib administration. The second PK blood sample (post-dose) will be obtained 1 to 3 hrs following administration of dabrafenib.

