2.1 Data analysis general information

Analysis datasets and outputs will be produced in the GPSII system using SAS version 9.4 (or later).

Data from all participating centers will be pooled prior to analysis. Subject accrual is spread thinly across centers and summaries of data by center would be unlikely to be informative and therefore will not be provided.

All data up to death or study withdrawal will be included in each analysis. Unscheduled visits will not be included in summaries, except to derive minimum/maximum post-baseline or on-treatment values. Unscheduled visits will be presented in subject listings.

Planned times relative to study drug dosing will be used in all tables and summary figures.

Unless otherwise stated, continuous variables will be summarized with n, mean, median, standard deviation, minimum and maximum, and categorical variables will be summarized with frequency counts and percentages.

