2.8 Pharmacokinetic endpoints

Summary statistics of concentration-time data for trametinib, dabrafenib and metabolites of dabrafenib (Hydroxy-dabrafenib and Desmethyl-dabrafenib) will be provided, both for the full PK population and separately for subjects from Japanese and non-Japanese race categories. Concentration-time data for trametinib, dabrafenib and its metabolites will be listed.

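### Afternoon PK samples drawn 4–8 h after a dose carry the pre-dose label, and the SAP's planned-time rule puts the pre-dose summaries at risk of upward bias

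*Protocol*

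**What the plan says.** Footnote 44 of protocol section 7.1 schedules two PK samples at Week 4. Morning-visit subjects withhold their doses. Their first sample, labelled pre-dose, falls 8 to 14 h after the previous evening's dabrafenib, and the second falls 1 to 3 h after dosing.

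For afternoon visits, "Subjects will be instructed to take their morning doses of study treatments as usual". The footnote continues: "The first PK blood sample (pre-dose) will be obtained 4 to 8 hrs following dabrafenib administration", and then "The second PK blood sample (post-dose) will be obtained 1 to 3 hrs following administration of dabrafenib". No dose other than the morning one is named for these subjects.

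Footnote 45 plans a single sample at each of Weeks 8 and 12, with both visits marked pre-dose. For afternoon attenders, "PK samples will be collected 4 to 8 hrs following dabrafenib administration".

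Two dosing instructions matter here. Section 6.3.1.1 says of dabrafenib: "Subjects should be encouraged to take their doses at 12 hr intervals and at similar times every day". Section 6.3.2.1 says of trametinib: "Subjects should be instructed to take their dose of trametinib concurrently with the morning dose of dabrafenib".

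SAP 2.1 states: "Planned times relative to study drug dosing will be used in all tables and summary figures". SAP 2.8 plans summary statistics of concentrations of dabrafenib, its metabolites and trametinib, "both for the full PK population and separately for subjects from Japanese and non-Japanese race categories". It names no split by morning or afternoon visit and does not define how PK times are coded. Protocol 12.2.1 requires the actual dates and times of samples and preceding doses to be recorded. Protocol 12.1 permits, but does not require, a population PK model.

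**The concern.** A row headed pre-dose will be read as a trough. Under these footnotes the same label covers morning samples taken at the end of a dosing interval and afternoon samples taken part-way through one. For trametinib the two kinds of sample are far apart in time since dose.

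The SAP's general rule directs tables to planned rather than actual time, and SAP 4.5 likewise reports data by nominal visit without windows. Applied as written to samples that share the pre-dose label, these rules most naturally put both kinds in one row. The resulting mean would depend on how many subjects attended in the afternoon as well as on the pharmacokinetics. The Japanese and non-Japanese summaries would inherit the same problem, and could differ for that reason alone if attendance patterns differed.

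The stake is the interpretability of the descriptive PK tables. ORR, the stopping rules, DoR, PFS, OS and the safety analyses do not use these data.

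**Working it through.** The plan states no PK figure to reproduce, so the check compares sampling windows and then shows a range under stated assumptions.

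**Step 1: order of the Week 4 afternoon pair.** Inputs: first sample 4–8 h after dabrafenib, second 1–3 h after dabrafenib (footnote 44); 12 h interval encouraged (6.3.1.1).

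- Both samples refer to the morning dose: the second (1–3 h) precedes the first (4–8 h), so the stated order fails.
- The second refers to a dose taken at the visit just after the first sample: the interval between doses is about 4–8 h, against 12 h in 6.3.1.1.
- The second refers to an evening dose at 12 h: the sample falls 12 + 1 = 13 to 12 + 3 = 15 h after the morning dose, which is 13 − 8 = 5 to 15 − 4 = 11 h after the first sample.

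The footnote states neither later-dose reading. On either one, the second sample follows no new trametinib dose, because trametinib is taken with the morning dabrafenib.

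**Step 2: gap in time since last dose between samples labelled pre-dose.**

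- Dabrafenib, Week 4: morning 8–14 h, afternoon 4–8 h. Gap: 8 − 8 = 0 h to 14 − 4 = 10 h; between midpoints, 11 − 6 = 5 h.
- Trametinib: morning about 24 h, afternoon 4–8 h. Gap: 24 − 8 = 16 h to 24 − 4 = 20 h; middle 18 h. These windows do not meet.

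**Step 3: size for dabrafenib.** Half-life and afternoon share are assumptions. With mono-exponential decline after the peak, the afternoon-to-morning ratio is R = 2^(gap / half-life). With afternoon share f, the pooled mean relative to the morning mean is 1 + f(R − 1).

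For a 6 h against a 12 h sample (gap 6 h) and f = 0.30:

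- Half-life 10 h: R = 2^0.6 = 1.516; pooled 1 + 0.30 × 0.516 = 1.155.
- Half-life 4 h: R = 2^1.5 = 2.828; pooled 1 + 0.30 × 1.828 = 1.548.

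The excess is about 15.5% to 55%. For the 5 h gap between midpoints, over a wider range of half-lives:

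| Assumed half-life | R | Pooled, f = 0.10 | f = 0.30 | f = 0.50 |
|---|---|---|---|---|
| 2 h | 5.66 | 1.47 | 2.40 | 3.33 |
| 4 h | 2.38 | 1.14 | 1.41 | 1.69 |
| 8 h | 1.54 | 1.05 | 1.16 | 1.27 |
| 12 h | 1.33 | 1.03 | 1.10 | 1.17 |
| 24 h | 1.16 | 1.02 | 1.05 | 1.08 |

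With zero gap or f = 0 the factor is 1.00.

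**Step 4: trametinib.** With an 18 h gap, assumed half-lives of 24 h and 120 h give R = 1.68 and 1.11. At f = 0.30 the pooled factors are 1 + 0.30 × 0.68 = 1.20 and 1 + 0.30 × 0.11 = 1.03.

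**Step 5: metabolites.** A metabolite may still be rising while the parent drug falls, so the decline model cannot be assumed and no direction follows from the documents.

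**The case against.** The strongest reply is that the SAP never says it pools these samples. SAP 2.8 uses neither the pre-dose nor the post-dose label, and for an afternoon visit the planned time relative to dosing is itself 4–8 h. The planned-time rule could therefore be read as keeping the groups apart. Time coding may also be settled in the lab manual or the table shells, which are not public. This stands as far as it goes: pooling is an inference. But the footnotes attach the same label to both kinds of sample, and nothing in the SAP prevents that label from becoming the table row.

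Three stronger readings are tempting and not supported.

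- A reader might infer that the pre-dose summaries *are* inflated. The documents give no half-life and no afternoon share, the dabrafenib windows meet at 8 h, and the bias can be nil.
- A reader might infer that the Week 4 afternoon schedule is impossible. It is out of order only if both samples refer to the morning dose. A later dose would restore the order, although none is named.
- A reader might infer that the race comparison is confounded. SAP 2.8 plans separate descriptive summaries without a test, and neither the number of Japanese subjects nor afternoon attendance by group is given.

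Nor can one say that these summaries are the only planned PK output. SAP 2.8 also lists the concentrations, a population model is permitted, and the public SAP text goes from 2.8 to 2.12.

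Finally, enrolment ended on 29-Jun-2018 and 12.2.1 says routine collection is no longer requested, so editing the footnotes cannot change samples already taken. That limits the remedy to the analysis and to documentation.

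**Conclusion.** The point holds as a risk of upward bias in the dabrafenib and trametinib pre-dose summaries, overall and by race group. It arises from a label that covers different times since dose combined with a planned-time rule that has no exception for PK.

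For dabrafenib the effect ranges from none to about 15.5–55% in the 6 h against 12 h illustration, which rests on mono-exponential decline, a 4–10 h half-life and 30% afternoon visits. Other assumptions give smaller or larger values, as the table shows. For trametinib the windows never meet, so some mixing effect is expected wherever afternoon samples are pooled, but its size again depends on quantities not given. The direction for the metabolites is open.

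The consequence is confined to descriptive PK. It is worth correcting because the stated rules can produce a misleading row and the data needed to avoid this should already exist.

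**What to change.** In SAP 2.8, exempt PK concentrations from the planned-time rule in 2.1. Summarise them by actual time since the last dose of the analyte concerned, using the times recorded under protocol 12.2.1.

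- Use bins that do not overlap and leave no gaps. For dabrafenib and its metabolites, for example: under 1 h, 1 to under 4 h, 4 to under 8 h, 8 to 14 h, and over 14 h. This covers 3–4 h and places 8 h in one bin only.
- For trametinib, count from the last trametinib dose and add a separate trough bin around 24 h, with its limits fixed before the tables are run.
- Label rows by hours since dose and do not report 4–8 h samples as pre-dose.
- Present the Japanese and non-Japanese summaries within bin.

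At minimum, split every summary by morning and afternoon visit.

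The sponsor should also reconcile footnotes 44 and 45 with sections 6.3.1.1 and 6.3.2.1, and document which dose the second Week 4 afternoon sample followed, so that data already collected can be interpreted.

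The cost is a short SAP change and one derived variable from recorded data. The downside is fewer subjects per bin, which will matter most for the smaller race group.

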7.2 Demographic/Medical History Assessments

The following demographic parameters will be captured: date of birth, gender, race and ethnicity. Medical/medication history will also be assessed as related to the eligibility criteria.

7.3 Critical Baseline Assessments

7.3.1 Baseline Confirmation of BRAF-Mutation Status

In order to be eligible for the study, subjects must also have archived tumor sample material available or be willing to undergo a biopsy in order to meet eligibility for the study.

If multiple results are available, eligibility should be based on the most recent test result. If the subsequent central laboratory testing is negative and, in the opinion of the investigator, the subject is deriving benefit, the subject may continue in the study.

For Solid Tumor Histologies:

For solid tumor histologies, archived tumor tissue sample or fresh tumor tissue sample obtained by biopsy must be submitted to the sponsor designated central reference laboratory for central confirmatory testing of the BRAF V600E mutation.

If sufficient archived tumor tissue is not available for central confirmation of BRAF mutation status and the subject cannot undergo a repeat biopsy to obtain an additional tumor tissue sample(s), the subject is NOT eligible for the study.

Table 5 BRAF V600E Mutation Testing Scenarios for Solid Tumors

	Scenario		Decision		
	Local BRAF V600E Mutation Test Performed? Result?	Archived Tumor Tissue Sample?	Tumor Sample to be Obtained	Eligible for Enrollment?	BRAF V600E Mutation Test to be Performed?
1	Yes. Positive	Not available	Fresh tumor tissue obtained by biopsy	Yes, only after submission of fresh tumor tissue sample for central testing	Yes, Central
2	Yes. Positive	Available	Archived tumor tissue	Yes, only after submission of archived tumor tissue sample for central testing	Yes, Central
3	No. No result.	Not available	Fresh tumor tissue obtained by biopsy	Yes, only if central test result on fresh tumor tissue is positive for a BRAF V600E mutation	Yes, Central
4	No. No result.	Available	Archived tumor tissue	Yes, only if central test result on archived tumor tissue is positive for a BRAF V600E mutation.	Yes, Central
5	Yes. Negative	Subject is not eligible for participation.			

For Hematologic Histologies:

For the HCL and MM cohorts, a fresh BM aspirate sample and a corresponding peripheral blood sample are required.

NOTE: For subjects in the HCL and MM cohorts, an archived tissue sample (such as formalin-fixed paraffin-embedded [FFPE] tissue sample from a BM biopsy), BM core

samples and BM clot samples are NOT acceptable for BRAF V600E testing. If a BM aspirate cannot be obtained due to a dry tap, please contact the Medical Lead.

Details on sample collection, processing, storage and shipping procedures are provided in the lab manual.

7.3.2 Baseline Documentation of Target and Non-Target Lesions for Solid Tumor Histologies

All baseline lesion assessments must be performed within 28 days of enrollment except where indicated differently in the T&E table (Section 7.1). Guidance on baseline documentation of target and non-target lesions will be provided in the SPM.

7.4 Safety

Safety assessments and procedures, including the timing of the assessments, are summarized in the Time and Events Table (Section 7.1). Additional time points for safety tests (such as vital signs, physical examinations, and laboratory safety tests) may be added during the course of the study based on newly available data to ensure appropriate safety monitoring.

7.4.1 Physical Examinations

Complete Physical Examination: A complete physical examination will be performed by a qualified physician, physician assistant or nurse practitioner under the supervision of a qualified physician, or another designee as permitted by local practices or laws. At minimum, the examination should include assessments of the head and neck, eyes, ears, nose, throat, skin, thyroid, CNS, lungs, cardiovascular system, abdomen (liver and spleen), lymph nodes, extremities and genitalia. Height (measured only at Screening) and weight will be measured and recorded. Complete physical examinations will be performed at Screening and at the post-treatment follow-up visit.

Complete physical examinations will also include thorough rectal and genitourinary (pelvic) examinations to assess secondary malignancies.

- **Rectal Examinations:** Including digital rectal examination and visual inspection of the anus and perianal area.
- **Pelvic Examinations (for female subjects only):** Including visualization of cervix. At Screening, pelvic examinations may be completed up to 24 weeks prior to date of first dose; thus, a subject's most recent gynecological examination may be used to satisfy the screening requirements. (Pap smear and/or colposcopy are not required unless clinically indicated.)
- **Brief Physical Examination:** A brief physical examination will include assessments of the lymph nodes, skin, lungs, cardiovascular system and abdomen (including liver and spleen assessment). Weight will be measured and recorded. Brief physical examination will be performed on Day 1 and every 4 weeks while on study treatment.

7.4.2 Dermatological Examinations

Dermatological examinations will be performed by an investigator or the subject may be referred to a dermatologist, at the discretion of the investigator. A complete or full body dermatological examination will be performed at the time points indicated in the Time and Event Table (Section 7.1) to identify any abnormal skin lesions. All abnormal findings (i.e.,

suspicious for proliferative skin lesions) will be identified and photographed during the Screening examination. Brief dermatological examinations should be performed every 4 weeks or more frequently if clinically indicated while on study treatment and every 4 weeks (± 7 days) for the first 6 months following treatment discontinuation. Wherever possible, the same individual should perform all of the examinations. Follow-up skin examinations by a referral dermatologist should be conducted if clinically indicated.

Biopsy in or around new skin lesions or lesions that change during the study is required if clinically indicated.

[REDACTED] A summary of the results should be submitted to the sponsor.

Skin photography of new lesions or lesions that change during the study must be obtained and forwarded to the sponsor. Refer to the SPM for details regarding skin lesion documentation by photography.

